9.9 Removal of Subjects

Subjects may withdraw from the study at any time at their own request. Subjects may be withdrawn from study drug treatment at any time at the discretion of the investigator or Vertex

for safety, behavior, noncompliance with study procedures, or administrative reasons. A subject who withdraws from study drug treatment will continue to be followed unless the subject withdraws consent.

Subjects will discontinue from study drug dosing and the investigator will notify the medical monitor if any of the following occur

- Pregnancy
- Meets any of the stopping (discontinuation) criteria (Section 9.8) or has other unacceptable toxicity as determined by the investigator

Subjects who are withdrawn from study drug dosing will complete assessments as described in Section 9.1.6 and may have additional PK samples collected as deemed appropriate by the investigator in consultation with the Vertex medical monitor. Consideration should be given to the need for additional safety assessments as described in Section 9.1.6. The investigator will use clinical judgment to determine whether assessments after study drug discontinuation should occur while the subject remains confined in the clinical unit or can be completed as outpatient visits.

Subjects who have been enrolled and whose screening *CFTR* genotype does not confirm study eligibility must be discontinued from the study, even if a previous *CFTR* genotype laboratory report was used to establish eligibility.

If a subject does not return for a scheduled visit, reasonable effort will be made to contact the subject. In any circumstance, reasonable effort will be made to document subject outcome. The investigator will inquire about the reason for withdrawal, request that the subject return all unused investigational product(s), request that the subject return for a Safety Follow-up Visit, if applicable (see Section 9.1.5), and follow up with the subject regarding any unresolved AEs.

If a subject withdraws consent for the study, no further assessments will be performed. Vertex may retain and continue using the study data and samples after the study ends, and may use the samples and information in the development of the study compound, for other drugs and diagnostics, in publications and presentations, and for education purposes. If a subject withdraws from the study, the study data and samples collected will remain part of the study. A subject will not be able to request the withdrawal of his/her information from the study data. A subject may request destruction of the samples collected from him/her during the study as long as those samples can be identified as his/her samples.

Stopping rules are presented in Section 9.8.

9.10 Replacement of Subjects

Subjects who withdraw or are withdrawn for nonsafety reasons during the study drug treatment periods may be replaced at Vertex's discretion.

10 STUDY DRUG INFORMATION AND MANAGEMENT

Study drug refers to VX-121, TEZ, VX-561, TEZ/IVA, IVA, and their matching placebos.

10.1 Preparation and Dispensing

Study drug may be dispensed only under the supervision of the investigator or an authorized designee and only for administration to the study subjects.

10.2 Packaging and Labeling

Vertex will supply the VX-121 tablets, TEZ tablets, VX-561 tablets, TEZ/IVA fixed-dose combination (FDC) tablets, IVA tablets, and all matching placebos. Study drug labeling will be in compliance with applicable local and national regulations. Additional details regarding packaging, labeling, and dispensing will be included in the Pharmacy Manual.

10.3 Study Drug Supply, Storage, and Handling

The investigator, or an authorized designee (e.g., a licensed pharmacist), will ensure that all investigational product is stored in a secured area, under recommended storage conditions, and in accordance with applicable regulatory requirements. To ensure adequate records, all study drugs will be accounted for via the drug accountability forms as instructed by Vertex.

VX-121 and matching placebo will be supplied as tablets of similar size and appearance containing 5 mg VX-121 and 0 mg VX-121, respectively.

TEZ and matching placebo will be supplied as white tablets of similar size and appearance containing 50 mg TEZ and 0 mg TEZ, respectively.

VX-561 and matching placebo will be supplied as tablets of similar size and appearance containing 50 mg VX-561 and 0 mg VX-561, respectively.

TEZ/IVA and matching placebo will be supplied as light yellow film-coated tablets of similar size and appearance containing 100 mg TEZ/150 mg IVA and 0 mg TEZ/0 mg IVA, respectively.

IVA and matching placebo will be supplied as light blue film-coated tablets of similar size and appearance containing 150 mg IVA and 0 mg IVA, respectively.

All study drugs will be stored in accordance with the drug label or the Pharmacy Manual.

10.4 Drug Accountability

The pharmacist or designated study site staff will maintain information about the dates and amounts of (1) study drug received; (2) study drug dispensed to the subjects; and (3) study drug returned by the subjects. Subjects will be instructed to return all used and unused materials associated with the study drug to the site. These materials will be retained at the site according to instructions provided by Vertex or its designee until inventoried by the study monitor. The study monitor will review study drug records and inventory throughout the study.

10.5 Disposal, Return, or Retention of Unused Drug

The study site staff or pharmacy personnel will retain all materials returned by the subjects until the study monitor has performed drug accountability. At the end of the study, the study monitor will provide instructions as to the disposition of any unused investigational product. If the study monitor authorizes destruction at the study site, the investigator will ensure that the materials are destroyed in compliance with applicable environmental regulations, institutional policy, and any special instructions provided by Vertex. Destruction will be adequately documented.

10.6 Compliance

To ensure treatment compliance, the investigator or designee will supervise all study drug dosing that occurs at the site. At each visit, site personnel will review that the subject is compliant with study drug dosing and remind the subject of study drug dosing requirements. Compliance will also be assessed by ongoing study drug count.

If a subject demonstrates continued noncompliance of study drug dosing despite educational efforts, the investigator should consider discontinuing the subject.

10.7 Blinding and Unblinding

This will be a double-blind study, with the exception of the Run-in and Washout Periods of Part 2, which will be open-label.

10.7.1 Blinding

All subjects, site personnel (including the investigator, the site monitor, and the study team), and the Vertex study team will be blinded to the treatment codes with the exception of the following:

- Any site personnel for whom this information is important to ensure the safety of the subject in the event of a life-threatening medical emergency
- Any site personnel for whom this information is important to ensure the safety of the subject or the male subject's partner and her fetus in the event of a pregnancy
- Vertex Global Patient Safety (GPS) and Regulatory Affairs personnel to satisfy serious adverse event (SAE) processing and reporting regulations
- Unblinded statistician preparing the final (production) randomization list who is not part of the study team
- Vertex IWRS Manager
- Vertex Clinical Supply Chain
- IDMC
- Vendor performing the unblinded analysis for any needed reviews of safety, PD, and efficacy data
- Bioanalytical contract research organization (CRO) analyzing PK samples and Vertex Bioanalytical personnel who are not members of the SET but review raw data from the Bioanalytical CRO. The Vertex Bioanalytical SET member will continue to be blinded.
- Vertex Modeling and Simulation personnel or vendor conducting the population PK and PK/PD analyses
- Vertex medical monitor may, for matters relating to safety concerns, unblind individual subjects at any time

The Vertex study team and lead investigator(s) will also conduct blinded reviews of all available safety and PK data after all subjects within a cohort complete the Day 29 Visit.

Sweat Chloride and Spirometry Blinding:

- During the conduct of the study, the Vertex study team will not have access to the spirometry or sweat chloride results after the morning dose on the Day 1 Visit.
- Sites, subjects, and their parents/caregivers/companions should not be informed of their study-related sweat chloride results during the Treatment Period regardless of whether the subject has prematurely discontinued treatment.
- Subjects and their parents/caregivers/companions should not be informed of their study-related spirometry results during the Treatment Period regardless of whether the subject has prematurely discontinued treatment.

A limited Vertex team independent of the study team may be unblinded and have access to safety, PD, and efficacy data for the purpose of conducting ongoing data reviews for planning and enabling clinical development, regulatory, and chemistry, manufacturing, and controls (CMC) decisions.

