8.1 Inclusion Criteria

1. Subject will sign and date an informed consent form (ICF).
2. Willing and able to comply with scheduled visits, treatment plan, study restrictions, laboratory tests, contraceptive guidelines, and other study procedures.
3. Subjects (male and female) aged 18 years or older on the date of informed consent.
4. Female subjects must have a negative serum pregnancy test at the Screening Visit.
5. Body weight ≥ 35 kg.
6. Subjects must be able to produce a valid (quantity-sufficient) sweat sample at screening. If the initial screening collection results in insufficient sweat volume, then the sweat chloride collection may be repeated once.

Subjects must have a sweat chloride value ≥ 60 mmol/L at screening or documented in the form of a laboratory report in the subject's medical record.

7. Confirmed diagnosis of CF as determined by the investigator.
8. Subjects must have an eligible *CFTR* genotype as noted below. If the screening *CFTR* genotype result is not received before the Run-in Period (Part 2) or randomization (Parts 1 [REDACTED] a previous *CFTR* genotype laboratory report may be used to establish

eligibility. Subjects who have been enrolled and whose screening genotype does not confirm study eligibility must be discontinued from the study (Section 9.9).

- Parts 1 [REDACTED] Heterozygous for *F508del* with a second *CFTR* allele carrying a mutation that does not produce a protein, or produces a protein that is not responsive to TEZ, IVA, or TEZ/IVA therapy (Appendix A)
 - Part 2: Homozygous for *F508del*
9. Subjects must have a forced expiratory volume in 1 second (FEV₁) $\geq 40\%$ and $\leq 90\%$ of predicted normal for age, sex, and height (equations of the Global Lung Function Initiative [GLI])⁸ at the Screening Visit. Spirometry measurements must meet American Thoracic Society/European Respiratory Society criteria⁹ for acceptability and repeatability.
 10. Stable CF disease as judged by the investigator.
 11. Willing to remain on a stable CF treatment regimen (other than protocol-specified changes in CFTR modulator regimen) through the Safety Follow-up Visit (Section 9.5).

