Note: Randomization will be stratified by ppFEV₁.

- ^a All subjects are required to complete the TEZ/IVA Run-in Period to establish a reliable on-treatment (TEZ/IVA) baseline.
- ^b The dosage of TEZ/IVA will be TEZ 100 mg qd/IVA 150 mg q12h, which will be administered as TEZ 100 mg/IVA 150 mg FDC in the morning and IVA 150 mg in the evening.
- ^c Part 2 will evaluate the same VX-121 dose (20 mg qd) used in Part 1. This dose may be adjusted downward based on emerging data from Part D of Study 001. The dosage of TEZ and VX-561 will be TEZ 100 mg qd and VX-561 150 mg qd.
- ^d The 4-week Washout Period is included to evaluate the effect on PD and efficacy endpoints as subjects step down from TC to TEZ/IVA, after the VX-121 washout.

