11.3 Pharmacodynamics: Sweat Chloride

Collection of sweat samples will be performed using the Macroduct[®] (Wescor, Logan, UT) collection device.

At each time point, 2 samples will be collected, 1 from each arm (left and right). Additionally, sweat collections will be performed on any single day during screening. At the Washout Visit(s) for all Parts, sweat chloride assessments should be done within 2 hours before study drug dosing in the morning. Collection of sweat chloride will not overlap with any other study assessments.

Sweat samples will be sent to a central laboratory for analysis of sweat chloride concentrations. Sweat chloride results for individual subjects will not be disclosed to the study sites.

Specific instructions for collection, handling, processing, and shipping of sweat chloride samples to the central laboratory will be provided in a separate Laboratory Manual.

See Section [10.7.1](#) for information about blinding of sweat chloride results.

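### The rule withholding spirometry results from subjects lapses at the end of the Treatment Period although blinded Washout data are still to come, and Protocol 10.7.1 and 11.3 disagree on sweat chloride

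*Protocol*

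**What the plan says.** Protocol 10.7.1 has three bullets on withholding results.

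- **Sponsor's study team:** "During the conduct of the study, the Vertex study team will not have access to the spirometry or sweat chloride results" once the Day 1 morning dose has been given.
- **Sweat chloride, for sites, subjects and companions:** they "should not be informed of their study-related sweat chloride results during the Treatment Period regardless of whether the subject has prematurely discontinued treatment".
- **Spirometry, for subjects and companions only:** "Subjects and their parents/caregivers/companions should not be informed of their study-related spirometry results during the Treatment Period". Sites are not named.

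Protocol 11.5.1 adds nothing on spirometry blinding beyond a reference back to 10.7.1. On sweat chloride, Protocol 11.3 states "Sweat samples will be sent to a central laboratory for analysis of sweat chloride concentrations" and then "Sweat chloride results for individual subjects will not be disclosed to the study sites". It gives neither a start nor an end to that restriction.

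On treatment blinding, Protocol 10.7 states "This will be a double-blind study, with the exception of the Run-in and Washout Periods of Part 2". The Part 1 Washout is therefore double-blind, and Figure 9-1 provides dual placebo for it. The Washout Periods (9.1.4) are separate from the Treatment Period (9.1.3) and follow it.

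**The concern.** The rule for subjects is shorter than the rule for the sponsor's study team two bullets above it, and shorter than the blinded part of the trial. As worded, nothing stops a subject from being told the Day 1, 15 and 29 ppFEV1 values after Day 29, before the Washout assessments.

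What follows is partly open to influence from the subject's belief about assignment: effort-dependent spirometry, one patient-reported questionnaire in Part 2, and adverse events elicited by questioning at each visit (Protocol 13.1.1.3). The Part 2 Washout also has a stated purpose: "The 4-week Washout Period is included to evaluate the effect on PD and efficacy endpoints as subjects step down from TC to TEZ/IVA". Washout and follow-up events count as treatment-emergent, because that period runs to 28 days after the last dose, Washout doses included (SAP 8.1). Safety is a primary endpoint.

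For sweat chloride the difficulty is that two sections give different rules. Taken literally, 11.3 also withholds the screening value from the site, although the site confirms eligibility (9.1.1) and inclusion criterion 6 reads "Subjects must have a sweat chloride value ≥ 60 mmol/L at screening or documented in the form of a laboratory report".

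**Working it through.** **1. The rules side by side**

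| Result | Withheld from | Ends | Source |
|---|---|---|---|
| Spirometry, sweat chloride | Sponsor's study team | End of study conduct | 10.7.1 |
| Spirometry | Subjects, companions | End of Treatment Period | 10.7.1 |
| Sweat chloride | Sites, subjects, companions | End of Treatment Period | 10.7.1 |
| Sweat chloride | Sites | No end (and no start) stated | 11.3 |

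The spirometry rule for subjects has no second source. The sweat chloride rule for sites has two sources that differ in duration. A site that obeys both receives nothing, and with a central laboratory there is no described route by which a result would reach the subject.

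**2. What is collected after Day 29** (Protocol Tables 3-1 and 3-2)

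- Part 1: spirometry, sweat chloride and PK at Day 47, which is 47 − 29 = 18 days after the rule lapses. No CFQ-R.
- Part 2: spirometry and sweat chloride at Days 43 and 57 (14 and 28 days after). CFQ-R at Day 57 only. The Washout drug is open-label.
- Both parts: adverse events through follow-up.

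Nominal adverse event collection in Part 1 from first dose is 29 + 18 + 28 = 75 days, of which 18 + 28 = 46 (61%) fall after the lapse. This is how long the gap lasts. It does not measure bias.

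**3. What is not affected**

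The ppFEV1 model uses Days 15 and 29 (Protocol 12.3.4.1; SAP 8.3.1.2). The sweat chloride and CFQ-R endpoints run through, or are at, Day 29. Later ppFEV1 enters only the descriptive by-visit summary in SAP 8.3.1.2. Safety is descriptive, without tests (Protocol 12.3.3; SAP 8.4).

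**4. How much one ppFEV1 change reveals**

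Inputs: mean change 7 and SD 8 (Protocol 12.1); planned numbers of 45 active and 9 placebo in Part 1, and 18 and 9 in Part 2 (Figures 9-1 and 9-2). Assumptions, not from the documents: zero mean change on control, the plan's 7 points for every active arm, and normal changes with the same SD in all arms.

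The probability that a treated subject's change exceeds a control subject's is Φ(7/(8√2)) = Φ(0.619) = 0.73, where 0.50 is uninformative.

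The best guess of an individual's arm also uses the allocation. Guess control when the change is below x₀ = 3.5 − (64/7)·ln(active/control).

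- Part 1: x₀ = 3.5 − 9.143 × ln 5 = −11.2. Correct guesses: (45/54) × 0.989 + (9/54) × 0.080 = 83.7%. Always guessing active gives 45/54 = 83.3%.
- Part 2: x₀ = 3.5 − 9.143 × ln 2 = −2.8. Correct guesses: (18/27) × 0.891 + (9/27) × 0.361 = 71.4%. Always guessing active gives 18/27 = 66.7%.

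The gain is 0.4 percentage points in Part 1 and 4.8 in Part 2 (unrounded). The documents give no sweat chloride effect or SD, so the same calculation cannot be made for that measure.

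**The case against.** The strongest reply is that no passage provides for releasing anything. Permission is inferred from where a prohibition stops, and 10.7.1 separately blinds subjects and site personnel to treatment codes with no end at Day 29. That stands as a description of intent. It does not close the gap, because a ppFEV1 value is not a treatment code, and the contrast with the study-team bullet shows that the protocol can state a longer duration when it means one.

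A reader might infer four stronger things that the documents do not support.

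- **That sites may receive and pass on sweat chloride results after Day 29.** Section 11.3 forbids disclosure to sites with no end date, so this is a conflict between sections and not a release. Nor is screening blocked outright, since criterion 6 also accepts a laboratory report already on file.
- **That subjects or investigators are in effect unblinded.** The gains of 0.4 and 4.8 points show weak inference from spirometry. Investigators were never barred from spirometry results, even during the Treatment Period, so the lapse adds nothing to their knowledge of ppFEV1 or to any effect of it on causality assessment.
- **That Washout CFQ-R is exposed throughout.** It is scheduled only at Part 2 Day 57, in an open-label Washout where only the earlier assignment remains to be guessed.
- **That the efficacy conclusions are at risk.** The scheduled data for those endpoints are collected by Day 29.

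**Conclusion.** The point holds in a limited form. The spirometry rule for subjects ends too early for a trial whose Part 1 Washout is double-blind, and the two sweat chloride rules contradict each other. The effect is confined to partial inference of assignment by subjects during Washout and follow-up. It bears on the Washout spirometry, the Part 2 Day 57 CFQ-R and subject-reported adverse events, none of which supports a planned hypothesis test.

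The size rests on the plan's 7 and 8 and on the assumptions in the working. A larger true effect or a smaller SD would make inference easier. Sweat chloride could be more revealing, but the documents give nothing with which to size it. This is an inexpensive improvement worth making, and it does not threaten the primary efficacy analysis.

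**What to change.** In both subject-facing bullets of Protocol 10.7.1, replace the restriction to the Treatment Period with: *from the first Treatment Period dose until the subject's last study visit*. In 11.3, limit the non-disclosure rule to results obtained after the first Treatment Period dose, with the same end point, and say that screening results go to the site for eligibility.

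The end point should be each subject's own last visit, not the unblinding of the part. Final analysis follows completion by all subjects and database lock (Protocol 12), and tying release to that could delay early enrollees far longer.

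The cost is a few sentences and a central-laboratory reporting setting. The added wait after Day 29 is nominally 18 + 28 = 46 days (6.6 weeks) in Part 1 and 28 + 28 = 56 days (8 weeks) in Part 2. It is shorter for Part 2 subjects who have no Safety Follow-up Visit under 9.1.5. Emergency unblinding under 10.7.2 is unchanged.

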10.7.2 Unblinding

At the initiation of the study, study site personnel will be instructed on the method for breaking the blind. The unblinding method will be either manual or electronic.

Unblinding of the individual subject's treatment by the investigator will be limited to medical emergencies or urgent clinical situations in which knowledge of the subject's study treatment is necessary for clinical management. In such cases, investigators will use their best judgment as to whether to unblind without first attempting to contact the medical monitor to discuss unblinding. If investigators deem it unnecessary to unblind immediately, they will first attempt to contact the medical monitor to discuss unblinding. If investigators have tried but are unable to reach the medical monitor, they will use their best judgment, based on the nature and urgency of the clinical situation, and may proceed with unblinding.

Contact information for the medical monitor (and an appropriate backup) is included in the medical monitoring plan.

If a subject's treatment assignment has been unblinded for a medical emergency or urgent clinical situation, the medical monitor will be notified within 24 hours of the unblinding event. The reason and the date of the unblinding will be documented clearly in the subject's study file. Information about the treatment assignment obtained from the unblinding will be maintained in a secure location with controlled access and will not be shared with Vertex, the CRO, or any site personnel (other than the physician treating the subject). In addition, the investigator will consider whether the clinical event that prompted unblinding will be considered an SAE, according to the regulatory definitions or criteria for SAEs, and if so, submit an SAE report to Vertex GPS or designee, per Section 13.1.2.

Vertex GPS or designee will also unblind any SAE reports in compliance with regulatory reporting requirements. In addition, Vertex may, for matters relating to safety, unblind individual subjects at any time.

